### 4.3 Clinical Evaluation Prior to Randomization

When patients are approaching the time for discharge, final study eligibility will be determined. Prior to discharge, clinical stability will be assessed to ensure resolution of signs and symptoms of acute HF. Blood pressure and resting heart rate will be assessed. Patients with a pre-discharge blood pressure of  $\geq 90/50$  mm Hg and heart rate  $\geq 70$  bpm will be eligible and approached for consent. Subjects should not have a planned/scheduled uptitration of beta-blocker in the following 4 weeks. Willing participants meeting entry criteria will provide written informed consent. Baseline heart rate must be  $\geq 70$  bpm on ECG or a 10-second rhythm strip.

[figure not shown]
PRIME-HF

---

[figure not shown]
#### **4.4 Randomization**

After signing the informed consent form, all subjects who fulfill all of the inclusion criteria and none of the exclusion criteria will be randomized. All patients will be randomized using an electronic system in a 1:1 allocation ratio to either pre-discharge initiation of ivabradine or usual care. Randomization will be stratified by clinical site.

## PRIME-HF

**Figure 1. Study Flow Diagram**

---

**Figure 2. Schematic of Study Design**
**Figure 2. Schematic of Study Design**

#### 4.5 Treatment Arms

The treatment arms for this study are pre-discharge initiation of twice-daily oral ivabradine (starting at 5mg BID with encouraged dose titration to 7.5mg BID) versus usual care (i.e., post-discharge initiation of ivabradine at discretion of routine physician) for 180 days.

#### 4.6 Patient Safety and Concomitant Medical Therapy

Patients will receive standard medical therapy throughout the study. Adjustments of background therapy can be made at any point during the study period at the discretion of the attending physician. Therapy may include diuretics, ACE-inhibitors or ARBs, neprilysin inhibition, beta-blockers, and mineralocorticoid receptor antagonists. Patients *may have adjustments of beta-blocker therapies up until 24 hours prior to randomization and still be eligible for the study*. Subject should not have a planned/scheduled uptitration of beta-blocker in the following 4 weeks.

PRIME-HF

---

Sites will report events of interest to include SAEs related to Ivabradine, Pregnancy, or lactation exposure. Additional details are found in Section 8.

---

## **5 STUDY PROCEDURES**

### **5.1 Screening and Prerandomization Procedures**

Potentially eligible subjects will be identified from inpatient admissions and screened by interview. Interested subjects will be asked to give written informed consent and undergo a screening evaluation to include a complete history, physical examination, and laboratory tests. Study personnel will assess each subject against each inclusion and each exclusion criterion, and the investigator will determine the subject's eligibility for study participation. The informed consent process and all assessments will be documented in the subject's medical record.

### **5.2 Baseline Evaluations**

At the baseline visit and the time of randomization (prior to administration of ivabradine), all study participants will undergo the following:

- History and physical examination
- Baseline heart rate assessment via ECG (if ECG not already obtained in screening)
- KCCQ and PGA

### **5.3 Treatment Intervention**

Participants randomized to pre-discharge initiation of ivabradine should receive the first dose of medication prior to discharge if possible. If ivabradine is administered and then discharge is delayed, participants should continue on open-label ivabradine until hospital discharge. Participants should then receive a prescription for outpatient ivabradine. Study drug will not be provided as part of the study. If the patient is randomized to pre-discharge initiation, the study team and/or inpatient care team (e.g., providers and care coordinator) should initiate the process to acquire outpatient medication, explore patient costs and consider support options for the patient. If the patient is not able to pay for the medication, they will continue in the study and will enter a registry of ivabradine-eligible

## PRIME-HF

---

patients with documentation of the medication acquisition challenges experienced by the patient and provider. All participants will be counseled on the signs and symptoms of bradycardia including lightheadedness, dizziness, and syncope. Participants will also be followed carefully for the remainder of the hospitalization and monitored for adverse events including bradycardia or recurrence of heart failure signs or symptoms.

## 5.4 Follow-up Evaluations

### 5.4.1 Clinical Follow-up Visit (Study Visit 1)

Consistent with current HF guidelines, all participants should have a follow-up study visit within 7-14 days of hospital discharge. The timing of this visit will be determined by treating physicians. Current medication use and doses, physical examination, heart rate, systolic blood pressure and quality of life (KCCQ and PGA) will be assessed at this clinical visit. For participants randomized to predischARGE initiation of ivabradine and on 5mg BID, the heart rate may be used to adjust the dose of ivabradine to 2.5mg BID or 7.5mg BID (Table 1). For participants randomized to usual care, ivabradine may be initiated at the provider's discretion. Participants not eligible for ivabradine at this visit will be documented and continue study follow-up.

**Table 1. Recommended Dose Adjustments for Patients Taking Ivabradine**

Heart Rate	Dose Adjustment
>60 bpm	Increase dose by 2.5 mg (given twice daily) up to a maximum dose of 7.5mg twice daily
50-60 bpm	Maintain current dose
<50 bpm or signs and symptoms of bradycardia	Decrease dose by 2.5mg (given twice daily); if current dose is 2.5 mg twice daily, then discontinue therapy

### 5.4.2 Clinical Follow-up Visit (Study Visit 2)

At 6 weeks (42 +/- 14 days) post-discharge, all participants will have follow-up study visit. The study visit will include an assessment of current medication use and doses,

## PRIME-HF

---

physical examination, heart rate, and systolic blood pressure. For participants on ivabradine, the heart rate may be used to adjust the dose (Table 1). For participants with a resting heart rate >60 bpm, the dose may be increased to either 5mg or 7.5mg BID. If the resting heart rate is <50 bpm or the participant is experiencing signs or symptoms related to bradycardia, then the dose may be reduced to 2.5mg BID or the study drug should be discontinued. If the heart rate is 50 to 60 bpm, then the dose may be maintained. For participants not yet taking ivabradine, then it may be initiated at the provider's discretion. Participants not eligible for ivabradine at this visit will be documented and continue study follow-up. Study investigators or designee will assess quality of life (KCCQ and PGA).

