## **2.5 Study Endpoints**

### **2.5.1 Primary Endpoint**

The study protocol (in section 10.1) states that the primary endpoint of the study is the proportion of participants using ivabradine at 180 days. The endpoint for each participant will be determined from ivabradine use at 180 days evaluated as a binary outcome.

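### Protocol section 5.4.2 contradicts Table 1, which it cites, on what to do for a participant on ivabradine 7.5 mg BID with heart rate below 50 bpm or bradycardia

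*Protocol*

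**What the plan says.** Protocol Table 1 sets dose changes by heart rate, relative to the current dose:

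- Above 60 bpm: "Increase dose by 2.5 mg (given twice daily) up to a maximum dose of 7.5mg twice daily".
- 50 to 60 bpm: no change.
- Below 50 bpm, or clinical bradycardia: "Decrease dose by 2.5mg (given twice daily); if current dose is 2.5 mg twice daily, then discontinue therapy".

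Protocol section 5.4.2, covering the week-6 visit, refers to Table 1 and then names target doses without tying them to the current dose:

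- Above 60 bpm: "the dose may be increased to either 5mg or 7.5mg BID".
- 50 to 60 bpm: "If the heart rate is 50 to 60 bpm, then the dose may be maintained".
- Below 50 bpm, or clinical bradycardia: "then the dose may be reduced to 2.5mg BID or the study drug should be discontinued".

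All three dose levels can occur by week 6. Treatment starts at 5 mg BID with titration to 7.5 mg BID encouraged (Protocol section 4.5), and section 5.4.1 allows a move to 2.5 or 7.5 mg BID at the first follow-up visit.

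On the primary endpoint, SAP section 2.5.1 states: "The endpoint for each participant will be determined from ivabradine use at 180 days evaluated as a binary outcome".

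**The concern.** Two instructions apply at one visit to one clinical finding, and for one dose level they prescribe different actions. A site that works from the table and a site that works from the text would treat the same bradycardic participant differently. Symptomatic bradycardia is the first event of interest listed in Protocol section 8.2.1, so the conflict falls where a clear instruction matters most.

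Whether the drug is reduced or stopped, and to what dose, also feeds several planned analyses:

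- time to ivabradine discontinuation in the competing-risk analysis (SAP section 11), where a stop counts when it happens;
- maximum dose and mean dose at 180 days (SAP sections 2.5.3 and 9.3);
- discontinuation for other symptoms (SAP section 9.3), depending on how the site records the event;
- possibly membership of the treated population, which SAP section 2.4 defines by receipt of ivabradine at the week-6 visit;
- the primary endpoint, but only through drug status at day 180.

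**Working it through.** The plan gives no figure on this point, so the check sets the two passages side by side for every combination of current dose and heart-rate band.

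Inputs: doses of 2.5, 5 and 7.5 mg BID (Protocol sections 4.5 and 5.4.1); the bands of Table 1; the actions in Table 1 and section 5.4.2. The literal reading takes the text's target doses as open to any current dose. It keeps only targets above the current dose when increasing (a participant already at 7.5 mg BID stays there) and only targets below it when decreasing.

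| Heart rate | Current dose (BID) | Table 1 | Section 5.4.2, literal | Result |
|---|---|---|---|---|
| >60 | 2.5 mg | 5 mg | 5 or 7.5 mg | text wider |
| >60 | 5 mg | 7.5 mg | 7.5 mg | agree |
| >60 | 7.5 mg | 7.5 mg | 7.5 mg | agree |
| 50–60 | 2.5 mg | 2.5 mg | 2.5 mg | agree |
| 50–60 | 5 mg | 5 mg | 5 mg | agree |
| 50–60 | 7.5 mg | 7.5 mg | 7.5 mg | agree |
| <50 or bradycardia | 2.5 mg | stop | stop | agree |
| <50 or bradycardia | 5 mg | 2.5 mg | 2.5 mg or stop | text wider |
| <50 or bradycardia | 7.5 mg | 5 mg | 2.5 mg or stop | no overlap |

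Count on the literal reading: 6 agree, 2 are wider in the text but contain the table's action, and 1 has no action in common; 6 + 2 + 1 = 9.

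Now read the text as shorthand for the table it cites: up from 2.5 to 5 or from 5 to 7.5; down from 5 to 2.5, or from 2.5 to stop. The two wider cells then agree, giving 8 of 9. The 7.5 mg BID step-down still conflicts, because no sentence in section 5.4.2 leads to 5 mg BID when heart rate is below 50 bpm.

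Link to the primary endpoint: visit 2 is centred on day 42 and the endpoint on day 180, so 180 − 42 = 138 days lie between them. SAP section 9.1 and Appendix 1 code use from the day-180 visit. A stop at visit 2 therefore gives use = 0 only if the participant is off drug at day 180, or is not assessed then and is coded as a failure whatever happened at visit 2.

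Size: the documents do not say how many participants were on 7.5 mg BID at week 6, or how many had heart rate below 50 bpm or clinical bradycardia. SAP section 2.3 gives 104 enrolled. Assuming an even split, 104/2 = 52 per arm, and one participant carries 1/52 = 1.9 percentage points of an arm's proportion. That is the weight of any single participant, not an estimate of this inconsistency's effect.

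**The case against.** The strongest reply is that section 5.4.2 sends the reader to Table 1 first and then only paraphrases it, so the table governs. This has force. It removes the 5 mg BID step-down and the above-60 bpm difference, and in every band both passages move the dose in the same direction. It does not remove the 7.5 mg BID case, where the paraphrase leaves out the table's action and offers two others.

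A second reply is that nothing here is binding. Table 1 is headed as recommended, the text mostly uses *may*, the trial is an open-label strategy comparison without supplied drug (Protocol section 5.3), and the treating physician's judgment takes priority (section 7.1). Variation between providers would indeed remain after any rewording. But the text uses *should* for discontinuation, and discretion does not explain two incompatible recommendations for the same participant.

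Three stronger inferences are tempting, and the documents do not support them:

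- That stopping at visit 2 is in itself a primary-endpoint failure. The endpoint is use at day 180, and the documents neither bar nor describe a restart.
- That only the text leads to stopping. Table 1 also stops the drug, from 2.5 mg BID; the literal text differs in allowing it from higher doses.
- That the inconsistency biases the comparison by a known amount or in a known direction. No frequencies are given, and step 8 of the study flow in the Executive Summary allows dose adjustment at this visit in either arm.

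**Conclusion.** Wrong as written, in one case on any reading: 7.5 mg BID with heart rate below 50 bpm or clinical bradycardia. Titration to that dose is encouraged, so participants can reach the case by week 6. In two further cases (5 mg BID with the same trigger, and 2.5 mg BID with heart rate above 60 bpm) the text is wider than the table only if read literally.

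This is more than a clerical slip, because both passages are operative dose instructions for a safety situation and they bear on discontinuation and dose outcomes. The effect on the primary endpoint is conditional on drug status at day 180, and its size cannot be computed from the documents. Nothing in them shows that any participant fell into the conflicting case.

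**What to change.** Reconcile Protocol section 5.4.2 with Table 1 so that one rule applies to each combination of current dose and heart rate. The clinical team must decide which rule; no view is taken here. If the text is meant only as a pointer to the table, its separate list of target doses needs to be removed or aligned. The cost is protocol wording and a note to sites.

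Enrollment stopped at 104 (SAP section 2.3) and SAP Addendum 2 refers to decisions after database lock and unblinding, so rewording cannot change how existing data were generated. For those data, add a descriptive table by arm of week-6 heart rate, ivabradine dose before and after the visit, and discontinuations, marking participants in the three cells that differ. Protocol section 5.5 schedules vital signs and medication at that visit, and SAP Appendix 1 takes ivabradine use and dose by visit from the usage data, so this needs only programming. Label the table as added after lock. Also state whether a participant who stops at the week-6 visit belongs to the treated population.

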**5.4.3 Phone Call**

At 90 (+/-7) days post-discharge, participants should be contacted by the site (phone call) to assess for event status, current medication use and doses, and tolerability of ivabradine, specifically

- Symptomatic bradycardia
- Symptomatic hypotension
- Other symptoms leading to ivabradine discontinuation

**5.4.4 Final Study Visit (Study Visit 3)**

At 180 (+/- 14) days post discharge, all participants will have a routine clinic visit. The visit will include an assessment of current medication use and doses, physical examination including heart rate assessment (by exam and 1 ECG), and systolic blood pressure. The final dose of ivabradine prior to the visit will be recorded. Participants never initiated on or eligible for ivabradine will also be recorded. The study investigators or designee will assess quality of life (KCCQ and PGA).

Using the study schedule of assessments, provider-determined heart rate will be assessed at the following time points: baseline, post-discharge clinical follow-up visit (within 7-14

PRIME-HF

---

days of hospital discharge), week 6, and day 180. Patient quality of life assessment will be assessed at the following time points: baseline, post-discharge clinical follow-up visit (within 7-14 days of hospital discharge), week 6, and day 180.

PRIME-HF

---

**5.5 Schedule of Assessments**

	Baseline				
Time (Day)	Pre-discharge	Day 7-14 post discharge	6 Weeks post- discharge (42 +/- 14 days)	90 Days post- discharge (+/-7 days)	180 Days post- discharge (+/- 14 days)
Visit	Baseline/Randomization	FU Visit 1	FU Visit 2	FU Phone Call	FU Visit 3
Subject consent	X				
Medical History	X				
Physical examination	X	X	X		X
Vital signs (HR,BP)	X	X	X		X
ECG	X				X
KCCQ	X	X	X		X
PGA	X	X	X		X
Medication assessment	X	X	X	X	X
Events of interest assessment		X	X	X	X

---

## **6 ENROLLMENT AND RANDOMIZATION**

### **6.1 Enrollment**

Eligible subjects who have given written informed consent and meet all inclusion and no exclusion criteria will be randomized.

### **6.2 Randomization**

After signing the informed consent form, all subjects who fulfill all of the inclusion criteria and none of the exclusion criteria will be randomized. All patients will be randomized using an electronic system in a 1:1 allocation ratio to either pre-discharge initiation of ivabradine or usual care. Randomization will be stratified by clinical site.

---

## **7 PARTICIPANT SAFETY**

### **7.1 Patient Safety and Concomitant Therapies**

This study will evaluate and compare pre-discharge initiation of ivabradine versus usual care in patients stabilized after an acute HF exacerbation requiring hospitalization. Although investigators are encouraged to follow the assigned treatment strategy, in all cases the patient's safety based on the clinical judgment of the treating physician will take priority over the specific treatment assignment. Concomitant therapies will be at the discretion of the treating physician. All subjects will receive standard of care which can be adjusted by their usual care provider(s) during the study according to clinical need. Usual care providers will be encouraged to follow the most up to date guidelines for cardiovascular care based upon local and institutional practice patterns and relevant published practice guidelines.

### **7.2 Institutional Review Boards**

All sites will submit the study protocol, informed consent form, and other relevant study documents to their Institutional Review Board (IRB) for approval.

### **7.3 Informed Consent**

All patients will have the purpose of the study, the study interventions and evaluations, and the potential risks and benefits of participation explained to them and their questions answered. If they consent to participation in this study, they will review and sign the informed consent form.

### **7.4 Study Discontinuation**

Subjects may withdraw at any time during the study without prejudice or be discontinued from study treatment at the discretion of the investigator if medically necessary. In addition, a subject may be withdrawn by the investigator or the sponsor if the subject violates the study plan or for administrative and/or other safety reason.

PRIME-HF

---

The investigator or designee will document in the eCRF when a subject has been discontinued or withdrawn from study treatment because of an adverse experience. When a subject discontinues or is withdrawn from treatment before study completion, all applicable activities scheduled for the final study visit should be performed at the time of discontinuation. Any adverse experiences that are present at the time of discontinuation/withdrawal should be followed by the site PI until resolution.

---

## **8 ADVERSE EVENT REPORTING AND FOLLOW-UP**

### **8.1 Safety**

In this study, all medications and procedures commonly used or performed as a part of standard of care for the management of HF have well-defined safety profiles. For this trial, defined clinical endpoints and events of interest will be recorded in the eCRF. In addition, events that are Serious and Unexpected will be reported by a site investigator to the local IRB per the IRB's instructions and will be the subject of a MedWatch report, based on local requirements.

The investigator is responsible for monitoring the safety of subjects enrolled into the study at the study site. The investigator or qualified designee will enter the required initial and follow-up information regarding events into the appropriate module of the eCRF. Investigators are to report serious adverse events in accordance with their local IRB requirements. Investigators should follow usual clinical practices at their institution for reporting to regulatory authorities serious, unexpected events related to standard of care medications and devices.

### **8.2 Definitions**

#### **8.2.1 Events of Interest**

Sites will record in the eCRF Events of Interest which include

- 1) Symptomatic bradycardia
- 2) Symptomatic hypotension
- 3) Other symptoms leading to ivabradine discontinuation
- 4) Any Adverse Event that, in the opinion of the site investigator, is related to ivabradine and is:
  - a) Serious, and
  - b) Unexpected

---

### **8.3 Protocol Specific Exceptions to SAE Reporting**

The following events will be collected in the CRF but are not the subject of a MedWatch report. These events will be captured on anticipated/disease related events pages, not on the SAE eCRF page. Anticipated, disease related-event in patients with acute decompensated heart failure include:

- Ventricular tachycardia
- Atrial fibrillation
- Myocardial infarction
- Acute coronary syndrome
- Acute renal failure
- Worsening heart failure
- Death

With the exception of the events listed above, all serious adverse events the site PI determines to be related to ivabradine must be recorded in the Serious Adverse Event eCRF and should be monitored until stabilization or resolution.

Site investigators are responsible for knowing the local requirements for prompt reporting of an adverse event to the reviewing IRB/EC and for reporting an SAE to FDA via a MedWatch.

An Independent Data and Safety Monitoring Board (DSMB) will review safety composite data at regular intervals throughout the study. The DSMB will be empowered to stop the study for evidence of harm but not for evidence of efficacy.

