## **8.6 Expectedness**

The Investigative site PI or designee will determine expectedness of an SAE according to the package insert for U.S. marketed ivabradine. Any SAE that is not identified in nature, severity, or specificity in the current study drug reference documents is considered unexpected. Events that are listed in the package insert as occurring with a class of drugs or as anticipated from the pharmacological properties of the drug, but not specifically listed as occurring with the particular drug under investigation, are considered unexpected. As per the ivabradine package insert, the most common adverse reactions occurring in  $\geq 1\%$  of patients are bradycardia, hypertension, atrial fibrillation and luminous phenomena (phosphenes).

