## **8.7 Adverse Event Reporting**

All SAEs obtained via direct subject reporting and/or clinical staff observation that the site PI determined to be related to ivabradine will be captured within the electronic case report form (eCRF).

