## **8.8 Serious Adverse Events**

The investigator must record, via the EDC system, all SAEs that the site PI determined to be related to ivabradine occurring at visit 1 through visit 3 within 24 hours of knowledge of the event. If the eCRF system is temporarily unavailable, notify the sponsor or designee of the event, including investigator-determined causality assessment, via a paper back-up SAE form. Upon return of the availability of the EDC system, the SAE information must be entered into the eCRF.

The investigator must record in the EDC system when important follow-up information (final diagnosis, outcome, results of specific investigations, etc.) becomes available after submission of the initial SAE information. Follow-up information should be submitted according to the same process used for reporting the initial event as described above (i.e.,

PRIME-HF

---

within 24 hours of knowledge, via the EDC system). All SAEs will be followed until resolution, stabilization, until otherwise explained.

Research sites are expected to follow local IRB policies and procedures for reporting AEs/SAEs.

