## **8.2 Adverse Events**

Adverse events (AEs) will be summarized for each randomization arm by body system and preferred term using MedDRA. The adverse events include events of interest, serious and unexpected events, and events which are related to ivabradine use in the opinion of site investigators. The summaries will show participant level and event level counts. Events will be sorted alphabetically by body systems and preferred terms. A data listing of adverse events will be presented.

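### The plan gives no like-for-like count of atrial fibrillation by arm, although the protocol names it as a common ivabradine reaction and collects it

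*Protocol*

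**What the plan says.** Protocol 8.6, citing the US package insert, puts AF among the most common reactions to ivabradine.

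Protocol 8.3 lists AF with six other anticipated, disease-related events. They are kept but rerouted: "The following events will be collected in the CRF but are not the subject of a MedWatch report", and "These events will be captured on anticipated/disease related events pages, not on the SAE eCRF page". The SAE rule that follows the list carves these events out even when they are attributed to the drug: "With the exception of the events listed above, all serious adverse events the site PI determines to be related to ivabradine must be recorded" on the SAE form.

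The next sections state the duty without that carve-out. Protocol 8.7: "All SAEs obtained via direct subject reporting and/or clinical staff observation that the site PI determined to be related to ivabradine will be captured" in the eCRF. Protocol 8.8: "The investigator must record, via the EDC system, all SAEs that the site PI determined to be related to ivabradine", within 24 hours of knowledge.

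SAP 8.2 promises a by-arm summary by body system and MedDRA preferred term. It names three categories: events of interest, serious and unexpected events, and "events which are related to ivabradine use in the opinion of site investigators". SAP 8.1 presents ECG rhythm by arm at baseline and day 180. SAP 10 lists five clinical events by arm, and AF is not one of them. Appendix 1 of the SAP names the datasets behind each endpoint. It identifies none of them as the anticipated-events pages and specifies no AF variable.

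**The concern.** Protocol 13.4.2 says the study will evaluate the safety of ivabradine after stabilization for acute HF. AF is both a plausible event of the disease and a labelled reaction to the drug, so only the comparison between randomized arms can separate the two. That comparison needs every AF event in both arms, whatever the site thought of its cause. The protocol collects the events on a page that the analysis plan does not say it will use.

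AF also affects another analysis. The SAP 2.5.3 footnote on appropriate participants excludes those with AF, judged on the day-180 ECG where there is one. AF can therefore remove a patient from the denominators of two tertiary ivabradine-use endpoints without its incidence being reported.

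**Working it through.** The documents state no figure for AF, so there is none to reproduce. The check is a trace of where an AF event goes.

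**1. Recording.** Under Protocol 8.3, AF goes to the anticipated-events pages, and serious related AF is exempt from the SAE page. Under 8.7 and 8.8, all related SAEs go into the eCRF/EDC, with no exception. A site can meet both by entering the event on the anticipated-events page. But the 24-hour rule and the page are then left to interpretation, and 8.6 treats as a drug reaction what 8.3 treats as disease.

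**2. Routes into a by-arm table.**

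| Route | AF it would catch | AF it would miss |
|---|---|---|
| SAP 8.2, related events | AF judged related, if the anticipated-events pages feed the table | AF not judged related |
| SAP 8.2, serious and unexpected events (Protocol 8.2.1, item 4) | Ordinarily none, because AF is in the package insert and so expected under 8.6 | Nearly all |
| SAP 8.2 and 9.3, other symptoms that end ivabradine | AF that stops the drug, if coded there | AF that does not stop the drug, and AF in patients not taking it |
| SAP 8.1, rhythm | AF present on the day-180 tracing | Paroxysmal or resolved AF, and patients with no day-180 ECG |
| SAP 10, clinical events | None by name; an AF admission counts only as all-cause hospitalization | All AF as such |

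Of the seven events on the 8.3 list, SAP 10 reports two by name: worsening HF and death.

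**3. How much the rhythm table covers.** Sinus rhythm is an entry criterion (Protocol 3.2), so the table amounts to one post-baseline snapshot. SAP 13.5 expects more than 10% of day-180 heart rates to be missing. Heart rate falls back on vital signs when the ECG is absent (SAP 13.1), so missing ECGs should be at least as frequent as missing heart rates. With 104 enrolled (SAP 2.3), 0.10 × 104 = 10.4, so on the SAP's own expectation at least 11 participants would have no day-180 rhythm.

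**4. Why a related-only count is not like for like.** A patient not taking ivabradine can hardly have AF attributed to it. As an illustration, take the planning rates of use at day 180 (50% and 35%, Protocol 10.2) as stand-ins for exposure. Suppose AF occurs at the same rate *r* in both arms, and sites attribute a fraction *f* of AF in exposed patients to the drug. The related-AF rates are then 0.50 × *r* × *f* and 0.35 × *r* × *f*. Their ratio is 0.50 / 0.35 = 1.43, an apparent excess of 43% with no drug effect at all. The actual exposure split is not in the documents. The point is that the ratio reflects exposure.

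**5. Size.** Assuming equal arms, 104 / 2 = 52 per arm. At the 1% floor, a fully exposed arm would have 0.01 × 52 = 0.52 drug-reaction cases. If only 50% are exposed, the figure is 0.01 × 26 = 0.26. The true rate may be higher, and the documents do not give it. They also give no background rate of AF in this population.

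**The case against.** The strongest reply has four parts.

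- **Related AF is in scope.** SAP 8.2 covers related events by arm and preferred term and does not limit itself to the SAE page or to serious events. SAP 8.1 adds rhythm by arm. This stands. A reader might infer that AF enters no SAP table at all, or that the trial would not report it by arm. The documents do not support either reading.
- **A separate page is not lost data.** Protocol 8.3 says the events are collected, and 8.7 and 8.8 require related SAEs to be captured. Being on the 8.3 list does not bar an event from the tables, since SAP 10 reports worsening HF and death. This also stands, but those two have named sources in Appendix 1 and AF has none.
- **The SAP may say more than can be seen.** SAP 8.2 uses a form of words that need not be exhaustive. One of the Appendix 1 datasets might hold the anticipated-events pages. The table shells and any first addendum are not in the text available. So an AF row elsewhere cannot be ruled out, and the finding is limited to what the SAP text specifies.
- **The routing is a defensible choice, and the counts will be tiny.** The drug is marketed and not supplied, the primary question is uptake, AF is expected under 8.6, and a DSMB reviews safety. This is fair as a reason for expedited-reporting rules. It does not bear on whether AF already collected should be tabulated by arm. Small counts limit precision and argue for a descriptive row, not for no row.

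**Conclusion.** The point holds in a limited form. The SAP text specifies no all-cause count of AF by arm for a reaction that the protocol itself calls common. AF judged related is nominally covered, but it depends on a data mapping the documents do not give. AF not judged related has no event row. The rhythm table is a single follow-up snapshot. Separately, Protocol 8.3 sits unreconciled with 8.6, 8.7 and 8.8.

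A reader might go further and infer that harm in the ivabradine arm is understated. The documents do not show this. Related AF that never reaches the table would lower that arm's count, while attribution that follows exposure would raise it relative to usual care. The net direction is unknown.

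The size is modest. Enrollment stopped at 104, and the protocol's 1% floor gives roughly 0.3 to 0.5 drug-reaction cases in the ivabradine arm, assuming equal arms and 50% to 100% exposure. Neither the actual rate nor the background rate can be derived. The gain is completeness of safety reporting, at almost no cost. No conclusion about the primary endpoint is affected.

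**What to change.** In SAP 8.2 or 10, add one row: participants with any AF within the 180 + 14 day window, by randomization arm, regardless of causality, with event counts alongside. Name the anticipated/disease-related events pages as the source in Appendix 1, and state whether those pages also feed the related-events table in 8.2. Present the row descriptively, without a p-value, given 104 enrolled; SAP 13.6 already treats analyses outside the named endpoints this way.

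SAP section 1 provides for a supplement or amendment, and Addendum 2 shows one made after database lock. If the row is added after lock, date it and label it as such.

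Reconcile Protocol 8.3 with 8.6, 8.7 and 8.8, so that it is clear where AF judged drug-related is recorded and under which reporting rule. With enrollment closed, this mainly clarifies the record. It cannot recover causality judgments that sites were not asked to enter.

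The cost is one extra table row with small counts and one clarifying clause. No new data collection is needed.
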